6.7 Does the research design require subjects to be deceived?

- No. All study subjects must be alive at the time of recruitment.

6.8 Will the subjects be exposed to any stress?

- No. Other potential psychological or emotional distress is described in detail in section 6.2.

7.0 Data and Specimen Banking*

- N/A.

8.0 Sharing of Results with Participants*

- N/A. This project does not involve investigational diagnostic tests, genetic tests, or incidental findings. We will not share any participant information with the participant's physicians.

9.0 Study Timelines*

9.1 The duration of an individual subject's participation in the study:

Aim 1 (community working groups): Eligible participants are: English-speaking, have a personal and/or family history of ovarian cancer, 25 years or older, have access to the internet and be available to attend in-person or online focus group discussions.

Participants will attend 2 to 3 90-minute in-person meetings and some additional outside "homework".

Aim 2 (message-based intervention (MBI) and waitlist standard outreach approaches): Eligible survivors are: diagnosed with ovarian, fallopian tube, or peritoneal cancers, lived in Georgia at the time of diagnosis, not deceased, and have a mailing address per the Georgia Cancer Registry (GCR)'s records. Study duration could be up to one year.

Aim 2 & 3 (post-intervention online survey): Survivors and relatives in both arms who login to the study website will be invited to complete an one-time online survey. Study duration could be up to 30 min.

Aim 3 (mail survey to survivors who did not login to the study website): GCR will send a brief survey with a \$10 incentive to survivors in both study arms who have never accessed the website after GCR completes recruitment efforts. Study duration could be up to 10 min.

Aim 3 (online discussion forum): We propose to purposefully sample survivors (~25) and relatives (~25) randomized to the MBI arm to participate in an online discussion forum. Study duration could be up to 1 hour.

Aim 3 (re-engagement of working groups, Year 4): After data analysis is complete (late Year 4), we will reengage community working groups from Aim 1 for a half-day workshop where we will report findings of the intervention and enlist additional feedback.

9.2 Totally duration of overall study: Four years.

10.0 Subject Population*

Aim 1 (community working groups): English-speaking, have a personal and/or family history of ovarian cancer, 25 years or older, have access to the internet and be available to attend in-person or online focus group discussions.

Aim 2 (message-based intervention (MBI) and waitlist standard outreach approaches): Survivors: diagnosed with ovarian, fallopian tube, or peritoneal cancers, lived in Georgia at the time of diagnosis, not deceased, and have a mailing address per the Georgia Cancer Registry (GCR)'s records. Relatives of survivors: able to read English, be 25 years or older, have access to

the internet, be a first- or second-degree relative of the survivor, and not be incarcerated or institutionalized.

Aim 2 & 3 (post-intervention online survey): Survivors and relatives in both arms who login to the study website.

Aim 3 (mail survey to survivors who did not login to the study website): **Survivors in both study arms who have never accessed the website after GCR completes recruitment efforts.**

Aim 3 (online discussion forum): Survivors and relatives randomized to the MBI arm who login to the study website.

11.0 Vulnerable Populations*

- N/A.

12.0 Local Number of Participants

1240

Planned (Anticipated)

Racial Categories	Ethnic Categories				Total	
	Not Hispanic or Latino		Hispanic or Latino			
	Female	Male	Female	Male		
American Indian/Alaska Native	4	1	0	0	5	
Asian	35	6	4	1	46	
Native Hawaiian or Other Pacific Islander	1	0	0	0	1	
Black or African American	302	53	33	7	395	
White	591	102	66	11	770	
More than One Race	18	3	2	0	23	
Total	951	165	105	19	1240	

13.0 Recruitment Methods

Aim 1 (community working groups): We will collaborate with local community organizations and use snowball sampling approaches to recruit 35-40 individuals to serve in study working groups. To be eligible, individuals must: speak English, have a personal and/or family history of ovarian cancer, be 25 years or older, have access to the internet and be available to attend in-person or online focus group discussions. In assembling the working groups, study staff will conduct additional eligibility screening (e.g., prior experience with cancer genetic services, family size) to increase the diversity of community members for working group activities. Georgia CORE Community Advisory Boards (CAB), the Cancer Patient Navigators of Georgia, and the Survivorship Advisory Board have extensive experiences working with cancer survivors across Georgia and will assist in recruitment for Aim 1 (See letters of support). [name] (Co-I) will oversee these activities with a research assistant and an ethics fellow. Two community consultants nominated by [name] will work with local organizations to recruit working group participants. Additionally, we will approach organizations where members are more likely to have undergone genetic counseling/testing and include male members to increase diversity on these characteristics. Participants will receive \$500 for attending 2 to 3 90-minute in-person meetings.

and some additional outside “homework”. Recruitment of community members will take approximately 3 months at the beginning of Year 1.

Aim 2 (message-based intervention (MBI) and waitlist standard outreach approaches): Ovarian cancer survivors in the Georgia Cancer Registry (GCR) database who meet the following criteria will be considered for study participation: 1) diagnosed with ovarian, fallopian tube, or peritoneal cancers; 2) lived in Georgia at the time of diagnosis; 3) currently are alive per the registry's records; and 4) have a mailing address. The proposed recruitment procedures comply with GCR's current standards and are adapted from strategies that were effective in other studies using cancer registry for recruitment.¹⁻⁵ We will classify survivors who log in to the study website as recruited. Recruitment will rely on multiple communications aimed to encourage survivors to log in to the study website; the number of contacts will be largely identical for both arms: first mail-out (full packet plus \$10 incentive), telephone contact from a trained GCR staff, second mail-out (postcard reminder), and third mail-out (full packet). Our review of registry files as of May 2019 showed that: of the 8,760 women with a diagnosis of ovarian, fallopian tube, or peritoneal cancer (excluding those who were deceased or lost to follow as of 2017), we will have addresses for about 2,918 survivors over the 16-month recruitment period. In a recent study using GCR to recruit breast cancer survivors in Georgia with registry standard mailing and phone contact without financial compensation, 63% agreed to participate.⁶ A conservative assumption of reaching (i.e., log in to the study website) 45% in the MBI arm versus 10% in the standard outreach arm, we need to recruit 801 cancer survivors into our study. Relatives of survivors eligible to participate must be: 25 years or older, have access to the internet, be a first- or second-degree relative of the survivor, able to read English, and not be incarcerated or institutionalized. We estimate that 801 cancer survivors will log in to the website and 75% of them (N=601) will enumerate a median of 2 at-risk relatives. We assume the number of at-risk relatives enumerated will not differ between intervention arms. Furthermore, we estimate that 40% of relatives referred by MBI arm participants will log on compared to 20% in the standard outreach arm. We expect that about 438 relatives will participate in the study. Recruitment of survivors and relatives for the intervention will occur in Year 2 and 3.

Aim 2 & 3 (post-intervention online survey): We will recruit survivors and relatives who logged on to the website, regardless of their level of participation. We will post a study invitation letter and a one-time 20-minute survey on the study website and send the letter to survivors and relatives with contact information (e.g., mailing address, email, or mobile phone number) about 4 weeks after the intervention phase. Based on our sample size scenarios we estimate recruiting 120 survivors (15% response rate) and 66 relatives (15% response rate) to complete the online survey. We will compensate participants with \$35 to complete the online survey. In other research, we have used an online survey to evaluate recall of B-RST™ results following a mammogram screening visit; 35% agreed to complete an online survey with a \$25 incentive.⁷ Recruitment of survivors and relatives for the online survey will take approximately 3 months at the beginning of Year 4.

Aim 3 (mail survey to survivors who did not login to the study website): GCR will send a brief survey to survivors in both study arms who have never accessed the website after GCR completes recruitment efforts. Based on our prior recruitment data, about 1,686 survivors will not visit the study website by Jan, 2023 and will be eligible for this survey. We will conduct staged selection

[figure not shown]

of 650 non-responders over the 8-month recruitment period (Jan – Aug 2023): (1) reach out to all participants with a confirmed phone number (GCR have talked to participants during trial recruitment or their voicemail states their name); 2) reach out to all participants with a confirmed mailing address (GCR confirmed the mailing address through at least two resources (GCR database, ACCUR or voter registration database); and 3) reach out to participants whose ovarian cancer diagnosis is within five years. We aim to recruit 375 survivors for this survey. The proposed recruitment procedures comply with GCR's current standards. Recruitment will rely on two rounds of communications aimed to encourage non-responders in both study arms to complete the survey (Figure 4).

The first mail-out packet will include a survey cover letter (See “non-responder survey cover letter”), \$10 cash, a postage-paid return envelope to return completed survey, and a 10-min survey (See “Non-responder survey draft”) that asks about participant recall of receiving study materials, perceived importance and relevance of learning ovarian cancer risks, privacy concerns about health website, and trust in university health research. Participants may answer the questions online by using a QR code or write their responses on the enclosed document and return it to GCR.

Two weeks after mailing each packet, GCR will contact survivors by phone who do not complete the survey online or by mail. We will call survivors every 2-3 days for up to 5 attempts, after which we will categorize them as inaccessible. The phone call aims to: 1) check on receipt of the survey packet; 2) offer survey completion by phone; 3) remind survivors to complete the survey by mail or online; and 4) answer questions regarding the study. This schedule is the standard for GCR outreach.

Figure 4. Recruitment Procedures for Non-responder Survey

Aim 3 (online discussion forum): We propose to purposefully sample survivors (~25) and relatives (~25) randomized to the MBI arm to participate. We will conduct cluster analysis based on 2/3rds of the recruited sample to assess patterns of website use and identify sub-groups of users. We will use multinomial regression analysis to understand sociodemographic differences

in cluster members and use the clusters as strata for the recruitment into the online discussion forum. These analyses will allow us to identify “user profiles” and stratify sampling to increase representation of various user patterns based on GCR contact effort, website usage (high/low), and uptake of genetic counseling/testing (yes/no). We will send invitations and identify a back-up individual from the waiting list, should the original invitee decline. Participants will receive information about how to participate in the online discussion forum via email/mail/phone/website postings. Recruitment of survivors and relatives for the online discussion forum will take approximately 3 months at the beginning of Year 4.

All survey instruments used in the study will be developed in the 12-month planning stage. Prior to fielding the study, these instruments and related scripts will be submitted as an IRB amendment.

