B.2. Study Population: Study activities will take place in Georgia (GA), where about 615 women are diagnosed with ovarian cancer and about 395 die from the disease each year.²⁹ We propose a population-wide recruitment approach and will use Georgia Cancer Registry (GCR) to retrospectively identify, screen, and enroll all living ovarian cancer patients in GA, diagnosed between January 2005 and December 2017. GCR contains information on demographic characteristics, condition at time of diagnosis (e.g., stage, histologic types, and other clinical and

Figure 2: Intervention design flow chart

demographic variables), and treatment history of all cancer patients in GA.²⁹ Since 2001, the database excludes borderline (low malignant potential) neoplasms. We will consider women in GCR for study participation if they meet four criteria: 1) diagnosed with ovarian, fallopian tube, or peritoneal cancers; 2) lived in GA at the time of diagnosis; 3) are not deceased per the registry's records; and 4) have a mailing address. Our review of registry files as of May 2019 revealed: of the 8,760 women with a diagnosis of ovarian, fallopian tube, or peritoneal cancer, excluding those who were deceased or lost to follow as of 2017, we will have addresses for approximately 2,918 survivors during the 16-month recruitment period. GA is the 8th largest state with almost 10.5 million residents; 1.8 million (~17%)³⁰ residents live in rural areas.³¹ The state enjoys substantial racial-ethnic diversity: 32% of the state is Black or African American alone (4th largest African American population in the U.S.), 9.6% is Hispanic or Latino and 4.2% is Asian alone, 15% of the population lives in poverty, and 15% lack health insurance.³⁰

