B.4.1. First contact letter (MBI arm only): We will mail survivors in the MBI arm a one-page infographic (See "U01 MBI infographic draft") that includes a postage-paid return envelope to return their responses to three questions (See "U01 MBI three questions draft"). Responses will help us better understand information needs of families affected by ovarian cancer. Participants may answer the questions online by using a QR code, or write their responses on the enclosed document and return it to GCR. Responses will be anonymous and will not be linked to any personal identifiable information. We will not report participants' responses for research purposes and their responses will be reported on an aggregate level (e.g., number of envelopes returned).

[figure not shown]
B.4.2. First mail-out: This mailing will be sent approximately 7-10 days after mailing the first contact letter, we will mail to survivors in both arms \$5 cash as a token of appreciation for their attention, and a recruitment packet based on their arm assignment: targeted print material in the MBI arm versus standard study invitation letter in the standard outreach arm. GCR staff will mail recruitment materials in batches of about 172 every month. We will use Accurint, a LexisNexis database with coverage across the US, to obtain the most current address for registry survivors in an effort to maximize reach of the mailed material on the initial attempt. The materials will instruct participants to contact the toll-free registry telephone number with questions or concerns. Throughout recruitment, we will perform monthly checks to avoid

initiating contact with a recently deceased woman. To reduce unnecessary contact attempts by GCR, the intervention coordinator will provide GCR with the IDs of survivors who have logged in to the study website on a biweekly basis.

B.4.3. Telephone contacts: Studies show that interpersonal communications, such as a personal phone call, can increase clinical trial accrual when combined with informational handouts.⁴⁸⁻⁵³ Two weeks after mailing each packet, GCR will contact survivors by phone who do not log in to the study website. We will call survivors every 2-3 days for up to 9 attempts, after which we will categorize them as inaccessible. The phone call aims to: 1) check on receipt of the recruitment packet; 2) remind survivors to log in to the study website; and 3) answer questions regarding the study. This schedule is the standard for GCR outreach.

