Process Outcome Measures: Implementation reach, dosage, and fidelity is based on proportions and means/standard deviations for relevant quantitative variables (e.g., website access, number of visits/length, counseling session evaluation scores). Outreach approach's acceptability, barriers, facilitators, and perceived alignment with ethical principles will be based on descriptive analyses of *quantitative* survey responses (mail and online – e.g., the proportion of participants who vote "yes or no" and rate outreach as protecting autonomy and respecting family relationship (relational autonomy)). For *qualitative* responses on the online discussion forum, we will conduct qualitative content analysis using MaxQDA. We will identify distinct themes and categories related to each discussion topic, such as acceptability, and alternative contact strategies and best methods of supporting relational autonomy. Two study team members (led by [name]) will independently code five responses per discussion topic to ensure agreement of coding. Using a final codebook, a bioethics fellow and graduate assistants will conduct coding. We will systematically review all responses for the most commonly occurring themes and will identify representative quotes. The recorded counseling sessions (~70) will also be qualitatively coded to compare 4 measures by study arm: 1) session length in minutes, 2) verbal dominance (ratio of counselor to participant statements), 3) patient activation (number of patient medical, psychosocial, and lifestyle statements and questions), and 4) nonverbal affect assessed by a 6-point scale^{71,72} (low to high) reflecting both positive (interest, warmth, engagement, empathy, respectfulness and interaction) and negative affect (dominance and hurried for the genetic counselor, anxiety and distress for the patient).

As described in detail in section 19.0, confidentiality safeguards are in place during the following activities: recruitment, informed consent process, participation in study website, survey and online forum, data transportation, data analysis, and study finding reporting. Only the study ID number will be attached to data. In terms of reporting of study results, only basic sociodemographic identifiers (e.g., age, income, education) will be reported in aggregate.

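### Does the five-year diagnosis rule leave the third stage of the non-responder survey selection empty?

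*Combined protocol and SAP*

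**What the plan says.** Section 13.0 (Aim 3, mail survey) expects about 1,686 survivors not to have visited the website by January 2023. It plans a staged selection "of 650 non-responders over the 8-month recruitment period", January to August 2023, and aims for 375 completed surveys. The stages are:

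1. everyone with a confirmed phone number, meaning that the registry has spoken to the person or that the voicemail greeting gives her name;
2. everyone whose mailing address is confirmed in at least two sources (registry database, a commercial look-up, voter registration);
3. "reach out to participants whose ovarian cancer diagnosis is within five years".

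No date is given from which the five years run. Section 6.0 (B.2 Study Population) and Section 24.0 (Georgia Cancer Registry) both limit the trial to women "diagnosed between January 2005 and December 2017". Section 10.0 defines the survey population as "Survivors in both study arms who have never accessed the website after GCR completes recruitment efforts". The questionnaire "asks about participant recall of receiving study materials", among other things. Section 17.0 (Process Outcome Measures) says that acceptability, barriers, facilitators and "perceived alignment with ethical principles will be based on descriptive analyses of" the mail and online survey responses.

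**The concern.** The survey pool consists of randomized survivors, so it carries the December 2017 diagnosis limit. On the most natural reading, with the five years counted back from when the survey is fielded, no one in the pool meets the third criterion.

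That stage is also the only one that does not require confirmed contact details. If it is empty, or if the first two stages already fill the 650, a non-visitor with neither a confirmed phone nor a confirmed address has no way into the sample. The trial can produce such people: Section 6.0 (B.4.3) has the registry call "for up to 9 attempts, after which we will categorize them as inaccessible". They are plausibly the ones least likely to have received the mailings, and receipt is one of the things the survey asks about. The results would then describe non-visitors with confirmed details and could understate non-delivery as a reason for not logging in.

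**Working it through.** **The plan's own figures.** The 650 has no stated derivation and no breakdown by stage, so it cannot be reproduced. Two ratios follow from the text: 650 / 1,686 = 38.6% of non-visitors selected, and 375 / 650 = 57.7% expected to complete.

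**Calendar check.** Inputs: last eligible diagnosis 31 December 2017 (Sections 6.0 and 24.0); fielding January to August 2023 (Section 13.0); eligible diagnosis months 13 × 12 = 156. The cutoff is the reference date minus five years. Stage 3 holds the eligible months from the cutoff to December 2017.

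| Reference date | Cutoff | Eligible months | Share of 156 |
|---|---|---|---|
| 31 August 2023 (end of fielding) | 31 August 2018 | 0 (missed by 243 days) | 0% |
| 1 January 2023 (start of fielding) | 1 January 2018 | 0 (missed by 1 day) | 0% |
| January 2022 (assumed) | January 2017 | 12 | 7.7% |
| January 2021 (assumed) | January 2016 | 24 | 15.4% |
| May 2019 (registry file review in Sections 6.0, 13.0 and 24.0) | May 2014 | 8 + 36 = 44 | 28.2% |

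The arithmetic is right for a count from fielding. It depends wholly on the reference date, and no document ties the rule to any of these dates. Months are not survivor counts. With the high mortality that Section 6.0 describes, recent diagnoses are probably over-represented among living survivors, so the shares above may be too low.

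**Is stage 3 needed to reach 650?** The documents cannot show that it is. A mailing address is an eligibility criterion, and B.4.2 already uses a commercial database to update addresses before the first mailing. A survivor whose registry address agrees with that database would meet stage 2. A survivor classed as inaccessible after nine calls can still enter stage 1 if her voicemail gives her name. Those left over have neither, and their number is unknown.

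**Does the selection contradict Section 10.0?** No. That section says who is eligible. Section 13.0 says that about 1,686 are eligible and openly selects 650 of them.

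**What would a random reserve cost?** Suppose 65 or 130 of the 650 packets went to a random draw from people not selected in stages 1 and 2, and that they completed at a fraction f of the planned rate (both are assumptions). Completed surveys = 375 − reserve × (375/650) × (1 − f).

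| Reserve | f = 1/2 | f = 1/4 |
|---|---|---|
| 65 | 375 − 18.75 ≈ 356 | 375 − 28.1 ≈ 347 |
| 130 | 375 − 37.5 ≈ 338 | 375 − 56.25 ≈ 319 |

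At up to five calls per extra non-completer, that is at most 18.75 × 5 ≈ 94 to 56.25 × 5 ≈ 281 more call attempts.

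**The case for a change.** The best case for a change is that a selection rule should work as written. This one returns nobody on its plainest reading, and two registry staff members could choose different dates and get anything from 0% to 28% of the diagnosis months. A sentence would settle it. The stage at issue is also the only door for people without confirmed contact details, and nothing in the plan weights for their absence or limits the results accordingly. If the three stages were meant as successive filters and not as additions, an empty third stage would empty the whole sample.

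The missing date stands, as far as the visible text goes; Figure 4, on recruitment for this survey, is not shown. The rest is weaker. The filter reading does not fit a plan that contacts everyone in each of the first two groups and expects 375 completed surveys. The lack of a route for the unconfirmed group is mostly a consequence of putting confirmed contacts first, which Section 13.0 states openly and which makes sense when each packet carries $10 in cash. A reserve would not repair the gap in what is learned about delivery: a packet sent to a wrong address is not answered, so the people whose mail failed still could not say so. The registry's own record of mailings and calls (Section 6.3) bears on that question in part.

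**Conclusion.** No change to the plan follows. The calendar observation is correct: counted from fielding, the third stage is empty, by 1 to 243 days. But it identifies an unstated reference date and does not show that the rule is unworkable. Whoever draws the sample will see at once that a count from 2023 finds no one and will have to use an earlier date or stop after the first two stages. Either is acceptable for a descriptive survey with no hypothesis test specified for it. Who was selected, and so to whom the answers apply, can be described when the results are reported.

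How far the sample under-represents people without confirmed details cannot be computed, because no stage counts are given. The primary outcomes and their power are unaffected, since neither uses this survey. Redesigning the sample would exchange about 19 to 56 completed surveys, under the assumed response rates, for a group that includes the people mail cannot reach. That is a trade-off on which reasonable designers may differ. This conclusion assumes that the stages add to one another and that the missing figure does not set a different rule.
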